## Potential confounders and effect modifiers

The following list, based on available literature, presents known and potential confounders and effect modifiers in population-based influenza vaccine effectiveness studies (please also refer to DRIVE D4.1: Framework for analysis of influenza vaccine effectiveness studies).

The minimum set for a pooled analysis is marked with an asterisk(\*). If available and relevant, the other determinants may be used in individual study site analyses, and if possible, they will may be harmonised between the study sites for pooled analysis, by developing guidelines for harmonization according to availability of data and included in the generic study level SAP.

- Age\*
- Sex\*
- Number of healthcare visits 12 months prior to the study period describing a study subject's healthcare seeking behaviour\*
- Number of hospitalisations 12 months prior to the study period to be used as proxy for the severity of the chronic conditions\*

- Any chronic underlying conditions or if possible to define (like chronic pulmonary disease, cardiovascular disease, metabolic disorders, renal disease, treatment-induced immunosuppression and disease-induced immunosuppression, medically attended obesity .\*
- Influenza vaccination in previous influenza seasons (at least one)\*
- Contraindication to influenza vaccination
- Pregnancy
- Use of influenza antivirals
- Use of statins
- Pneumococcal vaccination
- Socio-economic status or applicable proxy
- Smoking behaviour or parental smoking behaviour (for subjects ≤18 years)
- (For children) Perinatal and congenital risk factors (e.g. birth weight and/or maturity at birth, perinatal factors, inborn errors of metabolism, relevant malformations and congenital syndromes)
- (For children) Number of siblings
- (For children) Adherence to the local childhood vaccination programme
- > Each study site to describe the factors included in the study & how these are identified.

The list will be updated based on results of DRIVE D2.2: Systematic review of the sources of confounding, bias and strategies to manage their impact in influenza vaccine effectiveness studies, due June 2018.

## Sources of information

Data will be collected using a standardised questionnaire/data collection form (see data collection section). The source(s) for the current and previous vaccination status and for collecting general data may include:

- hospital medical records
- consultation of the patient's vaccination card
- data from the patient's insurance company showing evidence of pharmacy delivery or reimbursement of influenza vaccine
- interview with patient or his/her family
- interview with patient's GP (according with rules for Vaccination Status Ascertainment)

- interview with patient's pharmacist
- vaccination register
- > Each study site to define the sources of information used for each variable collected

## **Data collection**

Data collection and entry will be conducted at the site level. Data will be collected using a standardised questionnaire/data collection form, administered by clinicians at the moment of swabbing. The questionnaire will be developed before the beginning of the study period according with the list of variables adopted at the study site level.

- > Each study site to describe the data collection tools used
- > Each study site to describe if and how informed consent is obtained

## Laboratory testing

Respiratory specimens will be collected from all eligible patients (ILI and/or SARI). We strongly encouraged the use of random sampling for primary care studies recruiting ILI (i.e. swabbing the first 3 ILI cases presenting to a GP on the second day of the week of practice) and all SARI cases (i.e. all SARI cases presenting at the Emergency department of an Hospital).

Laboratory confirmation should be done through one of the following laboratory tests: reverse transcription-polymerase chain reaction (recommended option), viral culture, and immunofluorescence or rapid influenza diagnostic tests. Each positive test result is to be classified by influenza type (A and B) and preferably also subtype/lineage (A/H1N1, A/H3N2, B/Victoria, and B/Yamagata).

- Each study site to describe the specimen collection (i.e. to include a description of the criteria and procedure for swabbing at the site level).
- > Each study site to describe the specimen storage & transport procedures
- Each study site to describe the laboratory tests used & the selection of specimens and the procedures for genetic and antigenic characterisation (see Annex 4 for an example of results presentation)
- Each study site to describe if the laboratory participates in QA/QC (Quality Assurance/Quality Control) schemes

## Sample size considerations

This section gives sample size considerations and formulates recommendations. These recommendations are meant to support the design of the case-control studies on IVE. Obtaining a minimum sample size is not a requirement for study participation. Details on the sample size calculations based on the minimal detectable VE as well as precision are given in Annex 3.

DRIVE recommends case-control studies based on 500 cases or more. However, studies with smaller sample sizes might still contribute to the power of the pooled analyses, provided that the study site is able to optimally harmonise its protocol with the other study sites to minimize the

between-study heterogeneity. In case VE estimates with unacceptable large CIs are obtained, it might be considered to not report these estimates.

Figure 1 presents the precision of the overall VE for number of cases varying from 200 to 4000 subjects, when assuming a true VE of 50%, a 'cases to controls' ratio of 1:1 and a total vaccination coverage of 5%, 20%, 50% and 70%. The number of cases per control is likely to vary (by definition of test-negative design). The calculations are based on an anticipated true VE of 50% as this is a conservative choice, requiring larger sample sizes compared to assuming lower/higher VE values. A case-control study based on 500 cases and a 1:1 'cases to controls' ratio will result in 95% CIs of the overall VE with a lower limit larger than 30% given a true VE of 50%, for coverages of >20%.

**Figure 1.** Precision of the overall VE expressed as the lower limit of the 95% CI, assuming a true VE of 50%, a 'cases to controls' ratio of 1:1 and a total vaccination coverage of 5%, 20%, 50% and 70%.

Figure 2 presents the precision of the brand-specific VE for number of cases varying from 200 to 4000 for the same parameter settings as above and additionally assuming the brand of interest accounts for 10%, 20%, 40%, 60%, 80% and 90% of the total vaccination coverage. A case-control study based on 500 cases and a 1:1 'cases to controls' ratio will result in 95% CIs of the brand-specific VE with a lower limit larger than 25% given a true VE of 50%, for brands covering 40% to 90% of the influenza vaccines when the overall vaccination coverage is 50% or more.

**Figure 2.** Precision of the overall VE expressed as the lower limit of the 95% CI, assuming a true VE of 50%, a 'cases to controls' ratio of 1:1, a total vaccination coverage of 5%, 20%, 50% and 70% and that the brand of interest accounts for 10%, 20%, 40%, 60%, 80% and 90% of the total vaccination coverage.

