## **Precision**

The precision refers to the level of sampling error. The standard error and consequently the width of confidence intervals (CI) are measures of precision. As the VE CIs are asymmetric, we express precision as the lower limit of the two-sided CI of the anticipated true VE, expressed in %. The precision can be derived starting from the anticipated true VE, the confidence coefficient  $(1 - \alpha/2)$ , the number of cases, the 'cases to controls' ratio 1:*r* and the overall vaccination coverage  $\gamma$ . Consider the notation as defined in Table 1, where *N* is the total number of subjects,  $N_d^+$  the number of cases,  $N_d^-$  the number of controls,  $N_e^+$  the number of vaccinated subjects,  $N_e^-$  the number of unvaccinated subjects and where *r* is the number of controls per case and  $\gamma$  is the coverage.

Table 1: Cross-tabulation of	f exposure a	and disease in a	case-control study
------------------------------	--------------	------------------	--------------------

	Diseased				
		Yes (cases)	No (controls)		
Exposed	Yes	a	b	$N_e^+ = N \gamma$	
	No	С	d	$N_e^- = N(1 - \gamma)$	
		$N_d^+$	$N_d^- = r N_d^+$	N	

Then, from the lower limit of the CI for VE estimates based on a case-control study, or

$$VE_{LL CI} = 1 - exp \left[ \log(OR) + Z_{\alpha/2} \sqrt{\frac{1}{a} + \frac{1}{b} + \frac{1}{c} + \frac{1}{d}} \right],$$
(3)

where OR = 1 - VE and where  $Z_{\alpha/2}$  is the standard normal z-score, it follows that the precision is determined for given values for *a*, *b*, *c* and *d*. From anticipated values for *OR*,  $N_e^+$ ,  $N_e^-$  and  $N_d^+$ , the

cell count a can be analytically derived as;

$$a = \left(\frac{1}{2}\right) \sqrt{\frac{x_1 + x_2 + x_3}{(OR - 1)^2}} + \frac{N_e^+ OR + N_e^- + N_d^+ OR - N_d^+}{2(OR - 1)},$$
  

$$b = N_e^+ - a$$
  

$$c = N_d^+ - a$$
  

$$d = N_d^- - b$$

where  $x_{1} = N_{e}^{+2} OR^{2} + 2N_{e}^{+}N_{e}^{-}OR - 2N_{e}^{+}N_{d}^{+}OR^{2} + 2N_{e}^{+}N_{d}^{+}OR$   $x_{2} = N_{e}^{-2} + 2N_{e}^{-}N_{d}^{+}OR - 2N_{e}^{-}N_{d}^{+}$   $x_{3} = N_{d}^{+2}OR^{2} - 2N_{d}^{+2}OR + N_{d}^{+2}$ 

We calculated the precision of the overall VE based on a two-sided 95% CI for case-control studies using 'cases to controls' ratio of 1:1, 1:2 and 1:4 with the total number of cases varying from 100 to 4000, while assuming overall vaccination coverages of 5%, 20%, 50% and 70% and overall VE of 20%, 50% and 70%.

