## **Concluding remarks and recommendations**

We make the following observations and recommendations based on our sample size calculations for single-site case-control studies;

- We recommend case-control studies based on 500 cases or more. A case-control study with 500 cases and a 1:1 'case to control' ratio will result in 95% CIs of the overall VE with a lower limit of >30% given a true VE of 50% and an influenza attack rate of 5%, for coverages of > 20%.
- Case to control ratios of 1:2 or 1:4 yield slightly more accurate estimates compared to a 1:1 case to control ratio.
- A case-control study with 500 cases and a 1:1 'case to control' ratio will result in 95% CIs of the brand-specific VE with a lower limit of >25% given a true VE of 50% for brands covering 40% to 90% of the influenza vaccines when the overall vaccination coverage is 50% or more.
- A case-control study with 500 cases and a 1:1 'case to control' ratio will result in a minimal detectable overall VE of 30-40% for coverages >20%.
- A case-control study based on 500 cases and a 1:1 'case to control' ratio will result in minimal detectable brand-specific VE of 30-40%, for brands covering 40% to 90% of the influenza vaccines when the overall vaccination coverage is 50% or more.
- A case-control studies based on 1500 to 2000 cases and a 1:1 case to control ratio will result in a minimal detectable VE of 18-20% for an overall vaccination coverage of 20% or more. Improvements in accuracy both in terms of minimal detectable VE and precision will be minimal when increasing sample sizes further
- In case the VE is expected to be low (< 20%), higher sample sizes are required to obtain VE estimates with acceptable precision.
- In case interest is in VE within subgroups, the sample size calculations should be done with respect to the subgroup-specific sample size.
- IMPORTANT: These are recommendations to support the design of case-control studies on (brand-specific) VE. Obtaining a minimum sample size is not a requirement for study participation.

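### A true VE of 50% is not the conservative case for precision: on the plan's own VE-scale metric, precision worsens steadily as VE falls, and a VE of 20% needs 1.9 to 2.3 times the cases

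*Combined protocol and SAP*

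**What the plan says.** The main-text section Sample size considerations recommends a size: "DRIVE recommends case-control studies based on 500 cases or more". It explains why 50% was taken as the planning value for VE with the words "as this is a conservative choice, requiring larger sample sizes compared to assuming lower/higher VE values". With 500 cases and as many controls, the precision it then claims is a 95% interval "with a lower limit larger than 30% given a true VE of 50%, for coverages of >20" per cent. The brand-specific precision in the same section uses the same settings.

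Annex 3, Precision, defines precision as the lower limit of the two-sided 95% confidence interval on the VE scale, gives formula (3) for it, and runs VE values of 20%, 50% and 70%. Annex 3, Concluding remarks and recommendations, repeats the 500-case recommendation ("We recommend case-control studies based on 500 cases or more"), but also states: "In case the VE is expected to be low (< 20%), higher sample sizes are required to obtain VE estimates with acceptable precision".

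**The concern.** The main text says that moving away from VE 50% in either direction reduces the number of cases needed. The closing remarks of Annex 3 say that a low VE increases it. Both cannot be right for the same precision metric.

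This matters because the document is a template for sites to adapt, and the section is offered as support for their study design. Taken at face value, the clause tells a site that the precision quoted for 500 cases is a floor whatever the true VE. The Background section notes that observed effectiveness varies from year to year, including through strain mismatch, and Annex 3 treats VE 20% as one of its own scenarios. In a low-VE season, a site relying on the clause would get a wider interval than it planned for.

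**Working it through.** **Inputs.** 500 cases and 500 controls (1:1, N = 1,000), VE 50% and a lower limit above 30%: main text, Sample size considerations. Two-sided 95% interval (z = 1.96), coverage 5/20/50/70% and VE 20/50/70%: Annex 3, Precision. VE 30% and 40% are added here as intermediate values.

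**Formula.** Annex 3 formula (3): LL = 1 - OR × exp(1.96 × SE), with OR = 1 - VE and SE = √(1/a + 1/b + 1/c + 1/d). The cells come from the Annex 3 closed form, with coverage applied to all N subjects.

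**Reproducing the plan's figure (VE 50%, coverage 20%).** The cells are a = 72.84, b = 127.16, c = 427.16 and d = 372.84, so SE = 0.1631. LL = 1 - 0.50 × exp(0.3197) = 1 - 0.50 × 1.377 = 31.2%. At coverage 50% and 70%, LL is 35.7% and 34.1%. All exceed 30%, as stated. At coverage 5%, which is outside the stated claim, LL is 9.0%.

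**Same 500 cases, other VE values.** Expected lower limit, with the distance from VE in percentage points in brackets:

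| True VE | Coverage 5% | 20% | 50% | 70% |
|---|---|---|---|---|
| 20% | -41.7 (61.7) | -9.2 (29.2) | -2.5 (22.5) | -4.9 (24.9) |
| 30% | -24.6 (54.6) | 4.3 (25.7) | 10.2 (19.8) | 8.1 (21.9) |
| 50% | 9.0 (41.0) | 31.2 (18.8) | 35.7 (14.3) | 34.1 (15.9) |
| 70% | 41.9 (28.1) | 57.8 (12.2) | 61.1 (8.9) | 59.9 (10.1) |

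The distance shrinks down every column, so VE 50% is not the worst case at any coverage. The reason is visible in the algebra: distance = OR × (exp(1.96 × SE) - 1). At coverage 20%, SE is 0.1586, 0.1631 and 0.1739 for VE 20%, 50% and 70%, so the bracket changes little (0.365, 0.377, 0.406), while OR falls from 0.80 to 0.50 to 0.30.

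**Cases needed for the distance that 500 cases give at VE 50%** (formula (3) solved for the number of cases, 1:1):

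| True VE | Coverage 5% | 20% | 50% | 70% | Ratio to 500 |
|---|---|---|---|---|---|
| 20% | 956 | 1,081 | 1,139 | 1,114 | 1.9-2.3 |
| 30% | 783 | 859 | 896 | 880 | 1.6-1.8 |
| 40% | 631 | 666 | 683 | 676 | 1.3-1.4 |
| 70% | 295 | 244 | 221 | 231 | 0.4-0.6 |

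**Other metrics.**
- Full interval width: matching it instead takes 1,091 to 1,230 cases at VE 20%.
- Log-OR scale: the order reverses. For the SE that 500 cases give at VE 50%, VE 20% needs 456 to 487 cases and VE 70% needs 531 to 610. VE 50% is still not the maximum.
- Coverage taken among controls only: LL at VE 50% becomes 28.7/35.4/35.2% at coverage 20/50/70%, and the VE 20% factor becomes 1.6 to 2.4. The direction is unchanged.

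**Cross-check with the minimal detectable VE.** With 500 cases, 1:1 and 80% power, the Annex 3 formula (taking the root with RR below 1) gives 38.0/29.9/31.2% at coverage 20/50/70%. This agrees with the 30-40% stated in Annex 3.

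**The case against.** The strongest reply is that the error sits in one justifying clause and changes no stated result. The lower limit above 30% is correct and is tied explicitly to a true VE of 50% wherever it appears. No success criterion, analysis or site-eligibility rule depends on it. Both the main text and Annex 3 say that a minimum sample size is not required to take part, and smaller studies are welcome for pooling. All of this stands, and it limits the consequence to wording and printed figures.

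A reader might go further and infer that the 500-case recommendation is itself unsound, or that the plan calls it conservative. The documents do not support that. The word is applied to the VE 50% assumption, and the recommendation also rests on the minimal detectable VE, which does not use that assumption.

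A reader might also infer that weak performance at VE 20% is concealed. It is not. Annex 3 gives a minimal detectable VE of 30-40% for 500 cases, associates 18-20% with 1,500 to 2,000 cases, plots VE 20% and warns about low VE. Nor do the documents show any site sizing its study in the belief that VE 50% is the worst case.

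Finally, pooling is done on the log-OR scale, where VE 50% is mildly conservative against lower values. That does not rescue the clause: Annex 3 declares the VE scale as its precision metric, and on the log scale higher values need more cases.

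**Conclusion.** The clause is wrong as written, and it conflicts with the low-VE remark in Annex 3. On the declared metric, VE 50% is conservative only against higher values. The shortfall depends on how low VE is: a factor of 1.9 to 2.3 at VE 20%, 1.6 to 1.8 at VE 30% and 1.3 to 1.4 at VE 40%. A blanket statement that lower VE needs twice the cases would therefore overstate it. At VE 20%, the expected interval from 500 cases includes zero at all four coverages. That describes the interval when the estimate equals the true value, not a certainty for every study.

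These results assume a 1:1 ratio, the Annex 3 cell counts with coverage over all subjects, and no covariate adjustment. This is a should-fix correction of wording and figures, with no effect on design or analysis.

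**What to change.** In the main-text Sample size considerations section:

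- Delete the clause calling VE 50% a conservative choice.
- State that precision on the VE scale worsens as VE falls, and that the precision quoted for 500 cases is conditional on a VE of about 50%.
- Beside the VE 50% result, print the 500-case lower limits at coverage 5/20/50/70%: -42/-9/-3/-5% at VE 20% and -25/4/10/8% at VE 30%. Add the cases needed for equal distance: about 960 to 1,140 and 780 to 900.
- Cross-refer to the Annex 3 remarks on low VE and on the minimal detectable VE.

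The cost is a protocol wording change. The VE 20% curves already exist in Annex 3; the VE 30% figures need one more run of formula (3). The 500-case recommendation can stay, with a less favourable but accurate description.

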#### Data management

Each study site is responsible for the data collection, data validation, and data management of their individual study. DRIVE has developed a generic data management plan (task 4.2.1) and set up the necessary infrastructure for data collection and analysis of the pooled data (task 4.2.2). To consult such documents go to http://www.drive-eu.org/index.php/results/deliverables/.

- Each study site to specify how data are collected (e.g. web-based, paper forms) and validated
- > Each study site to specify procedures of data management.
- Each study site to provide a codebook that includes the variable names, variable descriptions, and the coding of variable values, if not following the DRIVE procedures/codebooks/tools.
- Each study site to provide any checks in place in the data entry system to avoid mistakes in data entry, and whether source data verification was conducted and how.
- > Each study site to specify the data checking and cleaning process

Summary and frequency tables as well as visual representations of appropriate variables will be used to find implausible or missing values within the dataset. Checks for inconsistencies will be carried out (e.g. date of respiratory specimen collection before date of onset of symptoms). Ideally, these checks will be included in the electronic questionnaire in order to avoid inconsistencies in the data entry. These values will be checked against the questionnaires or queried with the hospitals. Any changes to the data will be documented and stored separately from the crude database. Any additional recording of data during data cleaning phase will be documented. A guide and/or an example file for data cleaning will be provided if needed.

#### Representativeness of subjects included in the study

Study teams to describe the potential limitations in terms of representativeness of the subjects included

The study includes ILI and SARI cases. Health-seeking behaviour (referring to how individuals use health services: e.g. the decision to access healthcare, time from onset of illness to consultation, the type of healthcare provider consulted and the compliance to recommended treatment) may differ by country depending on the case management strategy (e.g. recommendation of seeing a GP first). In some cases, the management strategy will have an impact on the delay between onset of symptoms and hospitalisation. This, in turn, may have an impact on the time lag between onset and respiratory specimen collection, and may affect positivity rates between study sites. Beside the collection of dates of onset/admission/respiratory specimen collection, health-seeking behaviour and case-management strategy should be described for each study and it should be noted how it may affect the VE estimates.

## **Statistical analysis**

This section describes the main principles for the study site level analysis. The details of adjustment for confounders and effect modifiers are attempted to be harmonised between the study sites. The amount of variables to adjust for, and the heterogeneity/homogeneity between the study sites will be optimised according to availability of data. For one-stage and/or two-stage pooling of data from several study sites, please also refer to the DRIVE D4.4: Generic statistical analysis plan.

#### **Demographics and baseline characteristics**

The baseline characteristics of the study participants will be described and tabulated for cases and controls separately and for vaccinated and unvaccinated subjects within each group (by brand, type and overall). The baseline characteristics of the cases and controls will be compared using the Fisher's exact test (in case of nominal variables for the baseline characteristics), Mann-Whitney test (in case of ordinal or non-normal continuous variables) or Student's t-test (in case of normal variables).

#### Measure of effect

The crude (or unadjusted) brand-specific IVE will be estimated as

$$VE = (1 - OR) \times 100\%$$
,

where *OR* denotes the odds ratio, comparing the odds of vaccination among influenza-positive study participants by the odds of vaccination among influenza-negative study participants. The 95% confidence intervals will be obtained as well.

Confounder-adjusted brand-specific IVE estimates will be obtained from multivariable logistic regression models, regressing the health outcomes of interest on exposure status, age, sex and the confounders of interest. In case of effect modifiers, an interaction term between exposure and the effect modifier will be included in the regression model or stratified regression analyses will be performed.

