## **Study period**

The seasonal assessment will start when the influenza virus circulation begins (first virus detected at the national/study site level) in the country/region and will finish at the end of the influenza season (no cases detected during 2 consecutive weeks or equivalent).

Each study site to specify the assessment period: the definition of the beginning, peak and end of the influenza period at the study site according to the information provided by the local influenza surveillance system (including information on the type of virus circulating and virulence of the virus)

For the joint analysis, a harmonised minimum period will be defined (e.g. from week 40 till week 20), but if needed, it will be extended to fully cover the vaccination campaign and the epidemic in each study site. Definition of shorter time periods (e.g. early, middle and end season) will be developed to take into account differences in influenza activity over time and probable development of immunity in unvaccinated population through encounters with the circulating viruses

For addressing the secondary objective of estimating influenza vaccine effectiveness over several seasons, multiple study periods will be combined.

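### Calendar time of symptom onset is in neither the confounder list nor the primary model, and two unreconciled study windows leave open whether pre-circulation controls enter and pull VE down

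*Combined protocol and SAP*

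**What the plan says.** The effect measure is VE = 1 - OR, "comparing the odds of vaccination among influenza-positive study participants by the odds of vaccination among influenza-negative study participants" (protocol, Measure of effect). Adjusted estimates come from "multivariable logistic regression models, regressing the health outcomes of interest on exposure status, age, sex and the confounders of interest".

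The confounders are listed under Potential confounders and effect modifiers, where "The minimum set for a pooled analysis is marked with an asterisk". The starred items are age, sex, healthcare visits, hospitalisations, chronic conditions and previous influenza vaccination. The unstarred items run from contraindication and pregnancy to siblings and adherence to the childhood programme. Neither group contains a calendar-time variable. The Sensitivity analyses section gives no example concerning calendar time or the window. Annex 4 pools the site estimates on the log scale and adds no time adjustment.

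The Study period section describes two windows. The first opens at local detection: "The seasonal assessment will start when the influenza virus circulation begins (first virus detected at the national/study site level". The second is for the joint analysis: "a harmonised minimum period will be defined (e.g. from week 40 till week 20", with the provision that, if needed, "it will be extended to fully cover the vaccination campaign and the epidemic in each study site". The text does not say which defines the primary analysis set.

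Under Definition of vaccination status, a person with no current-season record counts as unvaccinated. Those within 14 days of vaccination are left out of the primary analysis.

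**The concern.** In a test-negative study, the date of onset is related to both sides of the odds ratio. Coverage rises from zero as the campaign proceeds, and the chance of a positive test rises and falls with the epidemic. A patient who presents in week 41 with a non-influenza infection has had little chance to be vaccinated and little or no chance to be a case, yet would count as an unvaccinated control. Enough such controls lower the odds of vaccination among test-negatives, raise the OR and lower VE. Excluding people vaccinated within the past 14 days does not remove them.

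At stake are the primary brand-specific, type-specific and overall estimates. This is bias rather than imprecision, so a larger sample or more sites will not reduce it, and inverse-variance pooling carries it into the European estimate. Its size depends on each site's campaign and epidemic timing, so sites can differ for reasons unrelated to the vaccine.

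**Working it through.** **Step 1. The plan's own precision figure, as a yardstick.** Inputs from the sample size section and Annex 3: 500 cases, 1:1 ratio, true VE 50%, two-sided 95% CI. At 20% coverage the Annex 3 cell formulas give a = 72.8, b = 127.2, c = 427.2, d = 372.8. The standard error of log OR is √(1/a + 1/b + 1/c + 1/d) = 0.163, and equation (3) gives 1 - 0.5 × exp(1.96 × 0.163) = 31.2%. At 50% and 70% coverage the lower limits are 35.7% and 34.1%. The plan's statement of a limit above 30% is reproduced. The sampling margin below 50% is therefore 18.8, 14.3 and 15.9 points.

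**Step 2. Direction, in closed form.** Let f be the share of controls seen before circulation, c0 their coverage and C the later coverage. Control coverage is p = f·c0 + (1 - f)·C, and

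VE_obs = 1 - [(1 - VE)·C/(1 - C)] / [p/(1 - p)].

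Example: C = 20%, f = 20%, c0 = 0. Then p = 0.16, control odds = 0.16/0.84 = 0.1905, case odds = 0.5 × 0.25 = 0.125, OR = 0.656 and VE_obs = 34.4%.

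| C | c0 | f = 10% | f = 20% | f = 30% |
|---|---|---|---|---|
| 20% | 0 | 43.1% | 34.4% | 23.2% |
| 20% | C/2 | 46.7% | 43.1% | 39.0% |
| 50% | 0 | 38.9% | 25.0% | 7.1% |
| 50% | C/2 | 44.7% | 38.9% | 32.4% |

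The bias is downward throughout. The values of f and c0 are assumptions.

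**Step 3. Size, from a weekly model of expected counts.** Assumptions, none given in the documents: true VE 50%; linear uptake over weeks 41-49; bell-shaped epidemic peaking in week 4 (SD 2.5 weeks); people within 14 days of vaccination excluded; no other confounding. In each week, vaccinated cases are proportional to (vaccinated) × (epidemic) × (1 - VE), unvaccinated cases to (unvaccinated) × (epidemic), and controls to coverage × accrual. Counts are summed over weeks to give the OR without calendar time.

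| Controls and window | Cov. 20% | Cov. 50% | Cov. 70% |
|---|---|---|---|
| Flat accrual, weeks 40-20 | 32.8% | 24.8% | 10.5% |
| Winter-peaked (SD 5, centred week 3, baseline 0.2), weeks 40-20 | 41.6% | 38.1% | 31.9% |
| Winter-peaked (SD 4, centred week 4, baseline 0.1), weeks 40-20 | 45.3% | 43.3% | 39.8% |
| Flat, circulation weeks only, uptake complete first | 49.3% | 49.3% | 49.3% |
| Flat, circulation weeks only, uptake to about week 2 | 46.9% | 45.3% | 42.8% |
| Any of the above, Mantel-Haenszel by onset week | 50.0% | 50.0% | 50.0% |

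Other timings with flat accrual (epidemic SD 3 weeks, peak 13, 17 or 20 weeks after week 40, campaign of 8 or 12 weeks from week 40) give 29.5-40.5%, 19.5-35.2% and 1.9-26.7% over weeks 40-20. Restriction to circulation weeks then gives 43.8-50.0%, 41.2-50.0% and 36.4-50.0%; the low ends belong to the early epidemic that overlaps the campaign.

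**Step 4. Which controls do the damage.** In the flat model about 60% of controls fall outside circulation weeks, roughly 30% before and 30% after. Starting at week 50 and keeping everyone to week 20 gives about 49.8% at all three coverages. The early controls cause the bias; the late ones add almost none.

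**Step 5. Against the yardstick.** At 20% coverage the flat scenario loses 50 - 32.8 = 17.2 points, against a sampling margin of 18.8. The winter-peaked scenarios lose 50 - 45.3 = 4.7 to 50 - 41.6 = 8.4 points. At 70% coverage the losses are 39.5 points (flat) and 10.2 to 18.1 points (winter-peaked), against 15.9.

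**The case against.** A reader might infer that the plan commits to the wide window and will therefore be wrong by 17 to 40 points. The documents do not support that. Weeks 40 to 20 is an example for a period still to be defined, while the opening sentence of Study period starts at first detection. Annex 4 pools estimates obtained under site protocols, which points to the site window, although the Statistical analysis section still mentions one-stage pooling as well. The large figures also assume flat control accrual. The weekly swabbing quota suggested for GPs under Laboratory testing could produce something like it, but winter-peaked accrual is equally possible and roughly halves the loss or better.

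Nor do the documents show that sites will leave time out. This is a generic protocol to be adapted locally. Its confounder list is open to revision after a systematic review, and details are referred to other SAPs and deliverables that are not part of this document. Study period also foresees shorter periods to reflect changing influenza activity, in its joint-analysis paragraph.

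These points limit the size and the certainty. They do not close the gap. Nothing in the text commits any site to a time term. The shorter periods are undeveloped and appear as a stratification under Secondary objectives, and no adjustment rule is attached to them. The wide window is called a minimum, and the only change foreseen is an extension.

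Two further inferences should be resisted. The 60% of controls outside circulation weeks is not the biasing share; only about half of it is. Artificial heterogeneity between brands is plausible where roll-out dates differ, but no brand scenario was calculated.

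**Conclusion.** The concern holds in conditional form. Calendar time is missing from the named adjustment set, and the window that decides how much this matters is not settled. The direction is downward in every scenario where early controls enter and uptake is incomplete.

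For a true VE of 50% at 20/50/70% coverage, the wide window gives about 33/25/10% with flat accrual and about 42-45/38-43/32-40% with winter-peaked accrual. With circulation weeks only, the loss is under one point when uptake is complete first. In the base epidemic it leaves about 43-48% when uptake overlaps circulation, and lower (36.4% at worst) when an early epidemic coincides with the campaign. All sizes rest on assumed accrual, epidemic and uptake curves.

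Exact recovery of 50% by week stratification follows from how the model is built. It shows that onset time carries all of this particular bias and says nothing about other confounding.

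**What to change.** 1. Add site-specific calendar time of symptom onset to the starred minimum set under Potential confounders and effect modifiers, and name it in the primary model under Measure of effect. Use a low-degree-of-freedom spline, or month or fortnight terms where data are sparse. Single-week strata over 33 weeks would need up to 32 parameters per site, too many for brand analyses at sites that may have fewer than 500 cases. Coarse blocks may leave a little residual bias when uptake is steep.

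2. Reconcile the two windows under Study period: state that the local circulation period governs the primary pooled analysis and keep the wider window for sensitivity analysis. Define the start so that one sporadic early positive does not reopen the window. This step is secondary, because adjustment for onset time removes the bias in these models without it, whereas restriction alone does not when uptake and circulation overlap.

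The cost is wording plus a few degrees of freedom per site. The onset date is already obligatory in the Annex 1 dataset, and subjects without it are already excluded. Controls dropped by the restriction carry almost no information once time is in the model.
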